Bivariate associations of communication scores with IAT scores will be estimated with Pearson or Spearman rank correlation coefficients depending on the distribution of the data. Generalized linear models (GLM) will be fit to the data to assess the associations of the IAT and racial attitudes with primary and secondary communication outcomes, while controlling for potential confounding variables including clinician age, gender and specialty. The identity link will be used in the GLM for continuous communication outcomes. Subgroup analysis will be performed in Asian, Black and Hispanic physicians if there are sufficient numbers in these groups to assess heterogeneity of the associations by race.

Power analysis:

The target sample size of 50 participants would have $>80\%$ power to detect a minimum correlation between IAT score and verbal dominance of $\rho \geq 0.38$ using a two-sided hypothesis test of a single correlation with a significance level of 0.05. This correlation is similar in magnitude to associations observed in prior studies; $B=11.0$ in one study and $r = 0.32$ in another.¹¹²

[figure not shown]
Protocol #

Phase 2:**Methods:**

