of group assignment. Block randomization will occur with randomly mixed block sizes of 2, 4, and 6. The allocator (research assistant) will hide block size from the executor (PI) in order to prevent the executor from predicting the next assignment. Randomization will be carried out by having a piece of paper that has the phrase “Intervention (Communication + Bias)” or “Control (Communication only)” placed inside an opaque envelope. The outside of the envelopes will be labeled with the sequence number. After a subject has been enrolled into the study and consented, the next sequence numbered envelope on the stack will be opened to determine the study group that the subject will enter.

Participants will be videotaped during high-fidelity simulations of encounters with caregivers described in phase 1, before and after receiving the intervention or control. The intervention and simulations will take place in one half-day workshop.

COVID-19 Concerns:

The Clinical Skills Center will be holding in-person simulations with standardized patients for the purposes of medical education starting in May 2021. The simulations in this study will not begin until after that time and will involve less risk than typical simulations because they will not entail a physical examination of the standardized caregiver. Actors and participants will be equipped with personal protective equipment including surgical masks. Trainers and participants in the training session will be required to wear provided surgical masks and remain six feet apart during the training sessions. If COVID-19 state or institutional guidelines prohibit these types of encounters at the time the simulations will be launched, the simulations and training will be adapted to a virtual format and nonverbal behavior coding will be adjusted. These changes will be submitted to the IRB as an amendment.

Study population and Recruitment:

Protocol #

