A new group of intensivists, oncologists, emergency medicine physicians and hospitalists will be recruited including resident and fellow trainees in those specialties. Physician subjects will be recruited face-to-face by the PI, through departmental email blasts and emails to contacts of the study team. As in phase 1, physicians will complete a screening questionnaire to exclude those that do not routinely encounter hospitalized patients with a life expectancy of less than one year. Potential subjects will be asked about the frequency and timing of previous communication and bias training. Physicians practicing Hospice and Palliative Medicine will be excluded because of their extensive prior training in communication.

Data collection:

Encounters will be videotaped. We will use the five-point verbal communication rating scale and nonverbal communication behaviors coded with the NAAS during the standardized encounter as described in phase 1 above.^{111,114} A research assistant who did not participate in the training sessions and is blinded to participant group will code communication behaviors. Subjects will complete the IAT and the questionnaire described in phase 1 immediately after the first encounter.

Outcome measures:

Subjects will complete an on-line questionnaire at the close of the session with Likert-type questions on the usefulness and acceptability of the training program and self-efficacy with cross-cultural communication. In addition, the questionnaire will include the cognitive and affective empathy portions of the Interpersonal Reactivity Index. For participants in the active group only, several questions will assess the illusion of ownership of the virtual body in the VR experience. An open-ended text box will invite feedback. The primary efficacy endpoint will be verbal dominance (ratio of clinician to patient speaking time during the encounter with a ratio of >1 meaning that the clinician dominated the discussion).⁹⁹ Secondary endpoints will include

Protocol #

verbal and nonverbal communication and encounter duration. Inter-rater reliability for the communication scores will be reported using Kappa values.

Analysis plan:

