Initially, the mean change in verbal and nonverbal communication scores pre- and post-intervention will be evaluated within each intervention arm using paired *t*-tests or Wilcoxon tests if the data are not normally distributed. To assess whether communication scores improved more in the bias mitigation treatment compared with communication training only control, a generalized linear model will be fit to the data with post-intervention score as the outcome, and pre-intervention score and intervention arm as the main effects. In addition, we will investigate whether pre-intervention level of bias modifies the effect of bias mitigation training, e.g., those with more bias will have a greater difference in improvement between the intervention and control group, by including in the model an interaction term between IAT score and treatment group on communication scores. A positive interaction will indicate that implicit bias as measured by the IAT modifies the effect of treatment group on communication score. With 25 subjects per intervention arm, the study will have 80% power to detect an effect size of 0.8 between groups in pre-post change in communication scores with a two-sided Type 1 error rate of 5%. While this is considered a large effect size according to Cohen's criteria, we would like emphasize that this is a pilot study in which the primary goal is to assess feasibility and to generate preliminary data on the effect of the proposed communication training intervention for clinicians to mitigate the effects of implicit bias.

$\Delta y = \alpha + \beta_0(Tx) + \beta_1(IAT) + \beta_2(Tx \times IAT) + \epsilon_1$, where Δy = change in communication score, Tx = treatment group

Data Management/Analysis:

Protocol #

Communication behavior codes and data from the questionnaires and IAT stored on Montefiore's secure Box drive and will only be accessible by members of the research team. Video recordings will be stored on a password-protected hard drive accessible only to the research team.

Risks/Benefits:

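### Phase 2 moderation analysis: the text adjusts for the pre-intervention score, but the displayed equation models change without it

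*Combined protocol and SAP*

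**What the plan says.** All of this is in the Combined protocol and SAP, Phase 2, Analysis plan.

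- **Arm effect.** "To assess whether communication scores improved more in the bias mitigation treatment compared with communication training only control", a generalized linear model is fitted "with post-intervention score as the outcome, and pre-intervention score and intervention arm as the main effects".
- **Moderation, in the text.** Whether pre-intervention bias modifies the training effect is examined "by including in the model an interaction term between IAT score and treatment group on communication scores". The only regression model described up to that point is the baseline-adjusted one.
- **Moderation, as displayed.** The equation is Δy = α + β0(Tx) + β1(IAT) + β2(Tx×IAT) + ε, and its left-hand side is defined as "change in communication score, Tx = treatment group". There is no pre-intervention score on the right.

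The plan does not call either form a sensitivity analysis or state which takes precedence.

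**The concern.** Writing Δy as post minus pre and moving the pre-score to the right gives y_post = α + 1·y_pre + β0·Tx + β1·IAT + β2·(Tx×IAT) + ε. The displayed equation is therefore the text's model with the pre-to-post slope fixed at 1 instead of estimated. Two analysts following the same plan could report different values of β2, with different standard errors, and the choice could be made after seeing the data.

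The second issue is precision. Fixing the slope at 1 leaves baseline noise in the outcome whenever the true slope is well away from 1. With only 50 participants, an interaction is already hard to estimate.

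**Working it through.** **The plan's own power figure.** "With 25 subjects per intervention arm", effect size 0.8 on pre-post change, two-sided 5%, stated power 80%.

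- Normal approximation: 0.8 × √(25/2) = 2.83; Φ(2.83 − 1.96) = 0.807.
- Noncentral t, 48 df: 0.791.

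The figure reproduces, and this point does not affect it.

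**Inputs for the comparison.** From the plan: 25 per arm, 1:1 allocation, two-sided 5%. Assumed, because the documents do not give them for Phase 2: pre-post correlation ρ, equal pre and post variances, and the correlation of the IAT with the scores. The last is set to 0 or to 0.38, which is borrowed from the Phase 1 Power analysis, where it is a minimum detectable correlation and not an estimate.

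**Large-sample formula, IAT unrelated to the scores.**

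- Residual variance of change: 2σ²(1−ρ).
- Residual variance after baseline adjustment: σ²(1−ρ²).
- Ratio: 2/(1+ρ), which is 1.54, 1.33, 1.18 and 1.05 at ρ = 0.3, 0.5, 0.7 and 0.9.

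**Simulation of β2.** 20,000 replicates per cell, unit variances, no true effects. Scenarios: (a) IAT correlated 0.38 with both pre and post; (b) IAT correlated 0.38 with pre, and with post only through pre; (c) IAT uncorrelated with both.

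| ρ | SD of β2, equation (a / b) | SD of β2, text's model (a / b) | Variance ratio (a / b / c) |
|---|---|---|---|
| 0.3 | 0.354 / 0.350 | 0.275 / 0.292 | 1.66 / 1.44 / 1.50 |
| 0.5 | 0.301 / 0.295 | 0.256 / 0.264 | 1.38 / 1.25 / 1.31 |
| 0.7 | 0.234 / 0.231 | 0.214 / 0.217 | 1.19 / 1.13 / 1.15 |
| 0.9 | 0.135 / 0.134 | 0.132 / 0.133 | 1.04 / 1.02 / 1.03 |

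Scenario (c) falls slightly below 2/(1+ρ) because the adjusted model spends one degree of freedom.

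**Minimum detectable interaction, 80% power.** (t₀.₉₇₅ + t₀.₈₀) × SD ≈ 2.86 × SD, in outcome SD per SD of IAT, scenarios (a) and (b):

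| ρ | Equation (46 df) | Text's model (45 df) |
|---|---|---|
| 0.3 | 1.00–1.01 | 0.79–0.84 |
| 0.5 | 0.84–0.86 | 0.73–0.76 |
| 0.7 | 0.66–0.67 | 0.61–0.62 |
| 0.9 | 0.38–0.39 | 0.38 |

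**Bias and power.** A separate simulation of scenarios (b) and (c) used 6,000 replicates and a true interaction of 0.8. Both models averaged 0.80. Power under the equation against the text's model was about 0.61 against 0.77 at ρ = 0.3, and 0.74–0.76 against 0.84 at ρ = 0.5.

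**The open choice.** With no true interaction, each model kept about 5% type I error, but the two disagreed on significance in about 2–6% of trials. Reporting whichever was significant gave about 6–8% type I error. At ρ = 0.5 the two estimates of β2 differed on average by 0.11–0.13 outcome SD per SD of IAT.

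**The case against.** The strongest reply is that nothing conflicts. The moderation sentence does not list its terms, it speaks of differing improvement, and the power statement is on change. The equation could then be the moderation model and the baseline-adjusted model the arm-effect model: two questions, two models. That reading is possible and may explain how the equation arose. It needs a less natural sense of *the model*, however, since only the baseline-adjusted model has been described when the interaction is added to it. It would also leave the usually less efficient form in place.

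The second reply is that the precision loss depends on quantities the plan does not state. This stands as a caveat. The loss depends on how far the true pre-to-post slope is from 1. If the post SD is 1.4 times the pre SD and ρ = 0.7, the slope is 0.98 and the variance ratio is 0.97–0.99, so the equation is marginally better. With the same SD ratio and ρ = 0.95, the ratio is 1.41–1.54. Over the unequal-variance settings tried, the equation gained no more than about 2–3% and often lost far more. The upper ends of the equal-variance ranges come from scenario (a) alone and should be read as illustrative.

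The third reply is that little depends on this. That is right, and it is why the point is minor.

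**Conclusion.** The concern holds, as a minor point. The text and the equation specify different models for the IAT-by-arm interaction, and the plan does not reconcile them. Neither is biased: arm is randomised and the IAT is taken before training. With equal pre and post variances, the standard error under the equation is larger by about 20–29% at ρ = 0.3 (square roots of 1.44 and 1.66), 12–17% at 0.5, 6–9% at 0.7 and 1–2% at 0.9. At high ρ the precision argument fades, but the choice between two models remains.

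The arm effect already has a stated baseline-adjusted model. It would lose precision, by the factor 2/(1+ρ) in variance, only if the equation were used in its place. Moderation is an additional analysis in a study whose stated primary goal is feasibility, and for ρ up to 0.7 either form detects only interactions of roughly 0.6 SD or more per SD of IAT.

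**What to change.** Replace the displayed equation with

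y_post = α + γ·y_pre + β0·Tx + β1·IAT + β2·(Tx×IAT) + ε

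or keep Δy on the left and add y_pre as a covariate, which gives the same β2. State that this model is used for β2 only and that the arm effect comes from the baseline-adjusted model without the interaction. Centring the IAT is optional: it leaves β2 unchanged and matters only if β0 from this model is to be reported as the effect at mean IAT.

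The cost is one line of the plan and one residual degree of freedom (46 to 45). No new data are needed. Participants are recorded "before and after receiving the intervention or control", and on the IAT the Phase 2 Data collection section says: "Subjects will complete the IAT and the questionnaire described in phase 1 immediately after the first encounter".

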The aim of this study is to assess the effects of clinician racial bias on end-of-life communication and to develop interventions to reduce the effects of implicit bias on quality of clinician communication. There are two study objectives: (1) Establish which communication behaviors in the end-of-life setting are most affected by clinician implicit racial bias and explicit stereotyping. (2) Pilot a theory-driven intervention to improve clinician communication and reduce disparities in quality end-of-life care. These objectives will be met in two study phases.

Methods/Design:**Phase 1:****Methods:**

(1) I will develop a case depicting a hospitalized 72-year-old with lung cancer and sepsis due to pneumonia on high-flow nasal cannula with my mentorship team of experts in palliative medicine and critical care. I will design a clinical encounter with the caregiver to discuss goals of

Protocol #

care. 2) The caregiver encounter will be piloted with critical care and hospitalist physicians at Montefiore to ensure realism and achieve standardization.¹⁰⁸ Black standardized caregivers will be recruited from the pool of actors used by the Einstein Clinical Skills Center. (3) Standardized caregivers will be trained in the use of a communication assessment tool.¹⁰⁹ (4) 50 physicians will be recruited to participate in a videotaped high-fidelity simulation of the encounter. The session will be followed by a 1-hour communication skills training to allow participants to earn continuing medical education (CME) credit. (5) Immediately after the simulation subjects will complete the IAT and a questionnaire probing for attitudes about race and end-of-life care along with demographic questions. We will assess training needs by adapting a previously developed questionnaire measuring physicians' self-identified serious illness communication training needs by incorporating questions about bias mitigation skills.¹¹⁰ The IAT is publicly available here: <https://implicit.harvard.edu/implicit/selectatest.html>.

COVID-19 Concerns:

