Encounters will be videotaped. The amount of time the physician and standardized caregiver speak will be recorded. A five-point verbal communication rating scale will be used to rate physician (1) informativeness, (2) supportiveness, and (3) partnership-building and a modified version of the Nonverbal Accommodation Analysis System (NAAS).^{89,111} The NAAS will be modified to include physical distance and open/closed body language which were shown to be important in serious illness encounters.⁷³ Verbal communication will also be analyzed from transcripts of the videotaped encounters. Coded verbal communication will be categorized as data gathering, emotion talk, partnership building, biomedical topics and decision-making content. Videos and transcripts will be coded in the secure Dedoose™ qualitative data coding software. An extra passcode will be added for a second layer of data security.

Another questionnaire will be administered at the end of the training. We will ask physicians to rate their experiences with different educational modalities presented in the training session, such as feedback from observed encounters, communication drills and role-plays. Open-ended questions will be used to gather formative information that the researchers may not have considered. This questionnaire will be distributed at the end of the communication skills training.

Protocol #

Outcome measures:

The primary endpoint will be verbal dominance (ratio of clinician to patient speaking time with a ratio of >1 , meaning that the clinician dominated the discussion). Empirical evidence links this communication measure to implicit bias and to patient-centered communication outcomes.⁹⁹ Secondary endpoints will include duration of the communication encounter, verbal communication ratings, nonverbal communication behaviors coded with the NAAS and standardized caregiver ratings. Inter-rater reliability will be reported using Kappa values.

Analysis plan:

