Protections against risks: Personal identifiers not be collected in the on-line instrument; instead a unique study ID will be assigned to each participant. Video recordings will be maintained in a password protected digital folder on a hard drive in a locked office. This database of coded communication scores will be stripped of participant identifiers as soon as all data is collected, and a file linking the study ID and patient identifiers will be kept in a separate, password protected digital folder.

Debriefing: After completion of the on-line bias measurement instrument, the subjects will be shown a debriefing statement including full disclosure of the aims of the study and the intent to examine the relationship between implicit racial bias and stereotyping and communication behavior. This statement will include a reminder that they may discontinue participation at any time and request that their data be removed from the dataset without penalty. The PIs contact information will be provided.

Potential Benefits of the Proposed Research: Subjects are not expected to directly benefit from this research.

[figure not shown]
Importance of the knowledge to be gained: The information from this study will provide knowledge about the role of implicit bias and stereotyping in communication behaviors that have

Protocol #

profound effects on the quality of end of life care for black patients. It will also inform efforts to mitigate the effects of this bias in future studies.

Necessity of withholding information in the consent process: Withholding of complete information from the consent process is only acceptable if there is no reasonably effective alternative to achieve the goals of the research. In this case, knowledge of the intent to study implicit racial bias is likely to affect the way physicians communicate in the standardized patient encounter, thus invalidating the results of the study.

Figures:

References:

1. Chartbook on Health Care for Blacks. Part 1: Overviews of the Report and the Black Population. Agency for Healthcare Research and Quality, 2015. (Accessed June 21, 2019, 2019, at <https://www.ahrq.gov/research/findings/nhqrdr/chartbooks/blackhealth/part1.html>.)

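### In Phase 1 nothing keeps the IAT score and attitude responses from the people who rate the videos, so rater expectation could create or inflate associations with the judged secondary endpoints

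*Combined protocol and SAP*

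**What the plan says.** **Timing of the exposure.** Phase 1, Methods: "Immediately after the simulation subjects will complete the IAT and a questionnaire probing for attitudes about race and end-of-life care".

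**Coding.** Phase 1, Data collection has physicians rated on a five-point scale for informativeness, supportiveness and partnership-building. A modified NAAS is added that takes in physical distance and open or closed posture. On who codes and how, it says only "Videos and transcripts will be coded in the secure Dedoose™ qualitative data coding software", with an extra passcode for security. No Phase 1 coder is identified and no masking is mentioned.

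**Storage.** Data Management/Analysis: "Communication behavior codes and data from the questionnaires and IAT stored on Montefiore's secure Box drive", with access limited to the research team. No restriction within the team is given. Video recordings are kept on a separate hard drive.

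**Use.** Phase 1, Analysis plan correlates the communication scores with IAT and then fits adjusted models of the communication outcomes on IAT and racial attitudes. Phase 2, Methods says that any specific behaviours found in Phase 1 to be related to bias and stereotyping will be targeted in the intervention. If none are found, racial bias is addressed in general terms.

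**Phase 2.** Data collection: "Subjects will complete the IAT and the questionnaire described in phase 1 immediately after the first encounter", and "A research assistant who did not participate in the training sessions and is blinded to participant group will code communication behaviors".

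**Identifiers.** Protections against risks: the on-line instrument carries a study ID and no personal identifiers, and the file linking ID to identity is kept in a separate protected folder. Of the codes it says "This database of coded communication scores will be stripped of participant identifiers as soon as all data is collected".

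**The concern.** Supportiveness, partnership-building and body language are matters of judgement. A coder who knows that a physician scored high on racial bias may mark the same behaviour lower. In an observational analysis whose exposure is that score, such expectation contributes directly to the association being estimated. Adjusting for age, gender and specialty does not remove it. The planned kappa values would not reveal it either, because raters who share the same knowledge can agree with each other and still both be shifted.

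The first study objective is to find which communication behaviours are most affected by bias, and the behaviours identified become added targets of the Phase 2 training. A rating artefact could therefore steer part of the intervention.

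The protocol already takes this kind of threat seriously in two other places. It blinds the Phase 2 coder to arm, and it withholds the racial focus from physicians because knowing it would change how they communicate. Coder knowledge of the Phase 1 exposure is the route left open.

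**Working it through.** **1. Can a Phase 1 coder know the exposure?**

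| Step | What the plan gives | What follows |
|---|---|---|
| Exposure collected | Right after the encounter (Phase 1, Methods) | It exists when the physician leaves the session |
| Ratings made | From video and transcript (Phase 1, Data collection) | Coding comes later; this order is inferred, not stated |
| Masking | None stated for Phase 1 | No barrier by rule |
| Access | Codes, questionnaires and IAT data on one drive for the team (Data Management/Analysis) | No barrier by permission for a coder on the team |
| Analysis | Ratings correlated with IAT (Phase 1, Analysis plan) | A shift in ratings that follows IAT enters the estimate directly |

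Access is permitted; it is not shown to be used.

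**2. The plan's own Phase 1 figure.** Inputs from Phase 1, Power analysis: n = 50, two-sided alpha 0.05, correlation 0.38, power above 80%. By Fisher's z, power = Φ(atanh(r)·√(n−3) − 1.96). Here atanh(0.38) = 0.4001 and √47 = 6.856, so power = Φ(2.743 − 1.960) = Φ(0.783) = 78.3%. The bias-corrected version gives 79.1% and simulation of the t test 79.0%. The stated figure reproduces to within two points, so the same formula serves for the illustration.

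**3. False-positive rate if expectation induces a correlation.** Assume no true association and an induced correlation r. The documents give no value for r, so a range is shown. Rejection probability = Φ(atanh(r)·√47 − 1.96) + Φ(−atanh(r)·√47 − 1.96).

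| Assumed r | atanh(r)·√47 | Two tails | Rejection rate |
|---|---|---|---|
| 0 | 0 | 0.025 + 0.025 | 5% |
| 0.1 | 0.688 | 0.102 + 0.004 | 11% |
| 0.2 | 1.390 | 0.284 + 0.000 | 28% |
| 0.3 | 2.122 | 0.564 + 0.000 | 56% |

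A cross-check by simulation supposes that the coder shifts the rating by b SD per SD of IAT, which induces r = b/√(1+b²). For b = 0.1, 0.2 and 0.3, r is 0.100, 0.196 and 0.287, and the rejection rates are about 11%, 28% and 53%. Each rate is for one rated endpoint.

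**4. Does the same route reach Phase 2?** The Phase 2 model is Δy = α + β₀Tx + β₁IAT + β₂(Tx×IAT) + error. Suppose a coder who knows IAT but not arm adds b₁·IAT to the pre-training rating and b₂·IAT to the post-training rating. Then Δy gains (b₂ − b₁)·IAT. That term is the same in both arms, so it falls on β₁ and leaves β₀ and β₂ alone. If b₁ = b₂ it cancels. Simulation with 25 per arm, no true effect, 4,000 runs and shifts of 0.1, 0.2 and 0.3 per SD of IAT gave rejection rates for β₂ of 5.2%, 4.1% and 4.3%. The results were the same when the second shift was double the first. The model of post-training score adjusted for pre-training score gave 5.1%, 4.4% and 4.8%. All are close to the nominal 5%.

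**The case against.** The strongest reply is that this is silence in a short pilot protocol, not a stated procedure. Coding happens in separate software with its own passcode, videos sit on a different drive from the IAT data, IAT records carry only a study ID, and the link file is held apart. The plan never says that a coder opens the IAT files. This stands as far as it goes: coder knowledge is possible, not demonstrated. But these measures protect confidentiality from outsiders. They do not bar a team member who holds the study ID and has access to the drive.

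The percentages are also fairly challenged. They are simply the power of a correlation test at assumed values. The top value of 0.3 would mean that expectation alone nearly matches the prior association of r = 0.32 cited in Phase 1, Power analysis. They show sensitivity, not a forecast.

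The reach is limited too. Speaking-time ratio and encounter duration are timed. The Phase 2 training goes ahead whatever Phase 1 finds; Phase 1 only adds targets to it.

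A reader might infer two stronger things that the documents do not support:

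- **That late removal of identifiers unmasks coders.** When names leave the score database does not determine whether a coder knows an IAT score. Codes and IAT must share an ID to be analysed, and the coder sees the physician on video anyway. For the same reasons, labelling videos by study ID alone would mask no one.
- **That Phase 2 is equally exposed because IAT is the effect modifier there.** With arms randomised and the coder blinded to arm, a shift driven by IAT cannot differ systematically between arms. Floor or ceiling effects on a five-point scale could let a little through, but not materially.

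**Conclusion.** The point holds for Phase 1 and for the judged secondary endpoints: the verbal ratings and the NAAS nonverbal codes. The exposure is available before coding, coders are not masked to it, and shared access means that nothing prevents them from knowing it.

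The size cannot be taken from the documents. The range of 11% to 56% false positives per rated endpoint rests wholly on assumed induced correlations of 0.1 to 0.3, at n = 50 and two-sided alpha 0.05. It also rests on the inference that coding follows the IAT and on the possibility, not the fact, of coder access.

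The primary endpoint is largely protected because it is timed. The Phase 2 treatment effect and Tx×IAT interaction are not materially affected. No sample size or power figure changes. The change is still worth making, because it removes a route to bias at almost no cost in the analysis that serves the study's first objective.

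**What to change.** - **Phase 1, Data collection:** state that those who code videos and transcripts are blinded to IAT scores and questionnaire responses.
- **Data Management/Analysis:** hold IAT and questionnaire data in a folder that coders cannot open, and merge them with the communication codes only after the codes are locked. Record the lock date.
- **Phase 2, Data collection:** for consistency, extend the existing statement on blinding to group so that it also covers IAT and questionnaire data.

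The wording on identifiers under Protections against risks can stay as it is for this purpose.

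The cost is a folder-permission change and a lock date, with no extra staff or participants. The small downside is that IAT data cannot be explored alongside the codes until coding is finished.
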